8.1. Analytic Sample for DMC Reports

All subjects randomized more than six weeks prior to the DMC meeting date will be included in the analytic cohort for the upcoming DMC report, and all data collected up to four weeks prior to the DMC meeting date will be analyzed. This allows for two weeks lag time for submission of data from sites.

8.2. Algorithm

Shell tables with annotated algorithm for creating the tables to be included in the DMC report are kept on the CSP590 Study Central file on Sharepoint in the Statistics and Data Management folder. These tables are updated as the study progresses and revisions are requested by the DMC members.

8.3. Outline of DMC Reports

The report is divided into four sections to cover subject disposition, baseline assessment, follow-up assessment, and safety assessment. The “Open Session” report includes summary tables that are not aggregated by treatment group (i.e., blinded data), and the “Closed Session” report includes summary tables for safety assessment that are aggregated by treatment groups (i.e., unblinded data). Following is the list of tables to be included within each of these 4 sections. Revision to this list, if any, will be discussed at the first DMC meeting to be held within six months of the initiation of subject enrollment in the VA sites.

8.3.1. Section A: Subject Disposition (OPEN SESSION ONLY)

Figure A1. CONSORT Diagram for CSP590

Table A2. Enrollment by site

Figure A3. Enrollment by site

Figure A4. Projected Enrollment

Table A5. Form Completion, by Form Type

Table A6. Form Completion, by Site
Table A7. Protocol Deviations
Table A8. Early Study Terminations

8.3.2. Section B: Baseline Assessment (OPEN SESSION ONLY)

Table B1. Demographics
Table B10. Study Medication Adherence
Table B11. Side Effects

8.3.3. Section C: Follow-up Assessment (OPEN SESSION ONLY)

Table C1. Study Outcomes
Table C2. Columbia Follow-up – Repeat Attempts in Detail

8.3.4. Section D: Safety Assessment (OPEN SESSION ONLY)

Table D1. Rates of Non-Serious Related Adverse Events (NAEs), by site
Table D2. Rates of Serious Adverse Events (SAEs), by site
Table D3. Summary of Related Non-Serious Adverse Events
Table D4. Summary of Serious Adverse Events (Form B15)

8.3.5. Section D: Safety Assessment (CLOSED SESSION ONLY)

Table D1. Rates of Non-Serious Related Adverse Events (NAEs), by Site and Treatment
Table D2. Rates of Serious Adverse Events (SAEs), by Site and Treatment
Table D3. **Reported in OPEN SESSION only**
Table D4. Summary of Serious Adverse Events (Form B15), by Treatment
Table D5. Related Non-Serious Adverse Events by System Organ Class, by Treatment
Table D6. Serious Adverse Events by System Organ Class, by Treatment
Table D7. Deaths Reported, by Treatment

9. Analytic Tables not included in the Data Monitoring Committee Reports

Following analytic tables will be generated annually and made available to the study team, Upon request of the DMC at the initial meeting these tables will not be included in the DMC report.

Table X1. Military Service

Table X2. Medical and Psychiatric History

Table X3. MINI Module Assessment

Table X4. Baseline Physical Assessments

Table X5. Baseline Laboratory Results

Table X6. Baseline Psychiatric Measures

Table X7. Baseline Substance Use (SCID-SUD)

Table X8. Concomitant Medications

10. Sample Size and Power

CSP590 is targeted to enroll a total of 1862 subjects, and approximately 40% of the enrolled sample is expected to terminate early (i.e., 20% complete data loss), thereby resulting in an analytic sample of 1490 evaluable subjects. With the evaluable study sample equally allocated to the 2 treatment arms, the study is powered to detect at least a 37% reduction in the one year outcome event rate.

Expected event rates used in sample size estimation to achieve 90% statistical power for hypothesis testing were 15% re-attempt rate in the placebo group and 9.45% re-attempt rate in the lithium group. Justification for selecting these rates to estimate sample size and power are provided in the protocol.

The results for the primary outcome measure will be analyzed by a two-sided log-rank test to detect either a hazards ratio that exceeds $1/0.61=1.64$ or is less than 0.61, i.e., the test has 90% power to detect a hazard ratio of 1.64 or larger or 0.61 or less.

These estimations are adjusted for an O'Brien-Fleming stopping rule with one interim and one final test of hypothesis, and allow for an overall two-sided type I error of 5% for the hypothesis being tested. Hence, the interim primary hypothesis will be tested at $p=0.002$ level (allowing for 0.2% Type I error), and the final primary hypothesis will be tested at $p=0.048$ level (allowing for 4.8% Type I error).

Tables 2 below consider three scenarios for possible shift in statistical power, specifically (a) in the event that an intervention effect different from the projected 37% reduction is observed, (b) in the event that the sample size for the study falls either above or below the targeted 1490 evaluable subject mark, and (c) in the event that the event rate is below the expected 15% in the placebo group. This study will have greater than 80% statistical power at 5% overall error if the observed effect is as low as 33% reduction, if the final evaluable sample is as low as 1200 subjects, or if we observe an event rate as low as 12% in the placebo group.

Table 2: Evaluation of variability in Statistical Power assuming 5% Overall Type I error.

(a) Change in statistical power for fixed sample size and a range of effect sizes

		Event Rates				
Evaluable N	N per arm	Placebo	Active	#Events	Effect	Power
1490	745	15%	11%	190	30%	73%
1490	745	15%	10%	188	31%	77%
1490	745	15%	10%	187	33%	81%
1490	745	15%	10%	185	35%	85%
*1490	745	15%	9.5%	182	37%	90%
1490	745	15%	9%	179	40%	94%

(b) Change in statistical power for fixed effect size and a range of sample sizes

		Event Rates				
Effect	Placebo	Active	Evaluable N	N per arm	#Events	Power
37%	15%	9.5%	1700	850	208	93%
*37%	15%	9.5%	1490	745	182	90%
37%	15%	9.5%	1400	700	171	88%
37%	15%	9.5%	1200	600	147	83%
37%	15%	9.5%	1100	550	134	79%
37%	15%	9.5%	1000	500	122	75%

(c) Change in statistical power for fixed effect and sample size and a range of event rates

Total N	N per arm	Event Rates		#Events	Effect	Power
		Placebo	Active			
*1490	745	15%	9.5%	182	37%	90%
1490	745	14%	8.8%	170	37%	88%
1490	745	13%	8.2%	158	37%	85%
1490	745	12%	7.6%	146	37%	82%
1490	745	11%	6.9%	134	37%	78%
1490	745	10%	6.3%	121	37%	73%

*Highlight indicates parameters proposed in CSP590

10.1. Interim Analysis

We will conduct one interim analysis after half of the participants have completed their 12 month follow up. This analysis is projected to take place approximately 2.5 years after initiation of enrollment (assuming it will take 1.5 years to enroll half the sample and allow 12 months of follow-up). After adjusting for attrition, a sample of 746 evaluable subjects, (373 in each group), is expected to be included in the analysis.

Projecting the same event rate in this sub-sample we expect to observe a 15% or 112 events (56 events in each group) under the interim null hypothesis that event rates are equal in the treatment groups. Under the interim alternative hypothesis, the absolute reduction from 15% to 5.3% is $(15-5.3) = 9.7\%$, the relative reduction is $(15-5.3)/15 = 65\%$, and the hazard ratio (treatment hazard rate/control hazard rate) is 0.34. The interim log-rank test is two-sided, and the interim null hypothesis will be rejected if the hazard ratio exceeds $1/0.34 = 2.94$ or falls below 0.34. Using the O'Brien-Fleming procedure, (Turnbull & Jennison, 2000), this analysis will have a Type I error of 0.2%.

We will confer with the Data Monitoring Committee members and the program leadership for potential stopping guidelines based on results from interim efficacy analysis.

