The formal hypothesis test is two-sided allowing for lithium augmentation therapy to be either more or less effective than placebo augmentation of enhanced suicide prevention management. However, the study of lithium will only be viewed as successful if patients augmented with lithium have a significantly lower hazard of repeated events than patients not treated with lithium.

We will test this hypothesis with a log rank test, followed by Cox proportional hazards regression modeling to provide the hazard rates, their ratio and the 95% confidence interval

about the ratios. We will also fit a random effects or frailty model to investigate potential heterogeneity of effect due to site variability (Glidden et al., 2004; Hougaard, 1991).

Interim Analysis

We will conduct one interim analysis after half of the participants have completed their 12 month follow up. Assuming a uniform rate of enrollment, it will take 1.5 years to enroll half the sample. Allowing for the last patient to accrue 12 months of follow-up, the interim analysis should take place approximately 2.5 years after initiation of enrollment, at which time, after adjusting for attrition, there should be a sample of 746 evaluable subjects, (373 in each group).

Projecting the same event rate in this sub-sample we expect a 15% repeat rate or 112 events (56 events in each group) under the interim null hypothesis that event rates are equal in the intervention and placebo groups. Under the interim alternative hypothesis, the absolute reduction from 15% to 5.3% is $(15-5.3) = 9.7\%$, the relative reduction is $(15-5.3)/15 = 65\%$, and the hazard ratio (treatment hazard rate/control hazard rate) is 0.34.

Using the O'Brien-Fleming procedure, (Turnbull & Jennison, 2000), this analysis will have a Type I error of 0.2%, which negligibly decreases the overall Type I error for the study and has virtually no effect on the power for primary analysis. The interim analysis is two-sided, and the interim null hypothesis will be rejected if the hazard ratio exceeds $1/0.34 = 2.94$ or falls below 0.34.

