4.3. Statistical Methods for Primary Efficacy Analysis

Primary efficacy analysis will include the modified intention to treat sample as defined in section 3.3 above.

The primary hypothesis can be stated as follows.

Under the null hypothesis: The 1-year event rate is 15% and the two treatment groups do not differ in their time to event hazard rates.

Under the alternative hypothesis: The 1-year event rate is 9.45% for patients treated with lithium and 15% for patients in the placebo group, resulting in an absolute reduction from 15% to 9.45% = 5.55% and a relative reduction of $(15 - 9.45)/15 = 37\%$. The group on lithium augmentation has a lower hazard rate than the placebo augmentation group with a hazard ratio for lithium therapy compared to control therapy lower than or equal to 0.61.

We will test this hypothesis with a two sided log rank test at 90% power and 4.8% Type I error (i.e., 5% overall error allows for one interim test at 0.2%). Null hypothesis will be rejected if the hazard ratio exceeds $1/0.61 = 1.64$ or falls below 0.61.

A significant difference showing that the lithium augmentation compared to placebo decreases the hazard of suicidal self-violence will be regarded as a positive result, whereas a result that shows lithium augmentation does not significantly differ from placebo or significantly increases the hazard rate relative to placebo will be regarded as a negative result.

Log rank test will be followed by Cox proportional hazards regression modeling to provide the hazard rates, their ratio and the 95% confidence interval about the ratio.

We will test the proportional hazards assumption by including a time*treatment interaction term in the model and use graphic methods to study goodness of fit as described in Anderson et. al., 1991.

The SAS code for the primary analysis is as follows, where, tx is coded as {1=lithium, 0=placebo}, event is coded as {1=adjudicated outcome, 0=otherwise}, and FUdays is counting number of days from randomization date to the first occurrence of (adjudicated outcome, death, 12 month date, or last study visit/contact date).

Log-Rank Test:

```
title "Survival Estimates by Month";
proc lifetest data=endpt plots=(s); time FUdays*event(0); strata tx; run;
quit;
proc lifetest data=endpt method=life plots=(ls) intervals=30 90 120 150
180 210 240 270 300 330 365; time FUdays*event(0); strata tx; run; quit;

title "Survival Estimates by Month";

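### The interim stopping rule is given as a method, a p-level and a hazard-ratio limit that contradict each other: O'Brien-Fleming at half information gives 0.0052, not 0.002, and HR 0.34 is a detectable effect, not a critical value

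*SAP*

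**What the plan says.** SAP section 10 adopts O'Brien-Fleming limits for two looks, "with one interim and one final test of hypothesis, and allow for an overall two-sided type I error of 5" (per cent). It sets the level of the first look explicitly: "the interim primary hypothesis will be tested at $p=0.002$ level (allowing for 0.2% Type I error"). The other look is assigned 0.048. Section 4.3 describes the split in these words: "5% overall error allows for one interim test at 0.2" (per cent).

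On timing, SAP section 10.1 says: "We will conduct one interim analysis after half of the participants have completed their 12 month follow up". It projects about 2.5 years from the start of enrolment, 746 evaluable subjects (373 per arm), and 112 events under the null. The interim alternative is 15% against 5.3%, HR 0.34. The same section attributes the level to the named method: "this analysis will have a Type I error of 0.2" (per cent).

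Both documents then turn the interim alternative into a decision rule. The protocol sentence containing "the interim null hypothesis will be rejected if the hazard ratio exceeds" sets the two limits at 2.94 and 0.34. SAP section 4.3 does the same at the final look, with rejection at HR above 1.64 or below 0.61. The protocol's sample-size subsection gives 0.61 and 1.64 only as effects that the test can detect, which is the correct use.

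**The concern.** A monitoring committee needs one boundary. Here the named method, the p-level and the hazard-ratio limit each imply a different one. With an observed HR of 0.50 on 91 to 112 events, the p = 0.002 rule rejects and the HR 0.34 rule does not. The endpoint is repeated suicidal behaviour, so it should not be left open which rule governs.

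The final look has the same problem. An observed HR of 0.70 with 182 events would be significant at 0.048, yet under the wording of section 4.3 the null would not be rejected.

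**Working it through.** **1. Inputs.** Overall two-sided 5%, levels 0.002 and 0.048, 1862 enrolled, 1490 evaluable, rates 15% and 9.45% (SAP section 10). Interim on 746 subjects, 112 events under the null, alternative 15% v 5.3% (SAP section 10.1). Uniform accrual (protocol, Interim Analysis) over 3 years (protocol, Executive Summary). Dropout of 40%, uniform over time (protocol, Missing Data from Attrition).

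**2. The plan's own figures.**
- 1862 × 0.8 = 1490; 746 × 0.15 = 112.
- HR = ln(1 − 0.0945)/ln(1 − 0.15) = 0.61.
- Final events = 745 × (0.15 + 0.0945) = 182.
- Power at level 0.048 with 182 events is 90.2% (Freedman) or 91.3% (Schoenfeld). Comparing two proportions with 745 per arm gives 90.3%.

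The fixed design reproduces.

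**3. O'Brien-Fleming levels at t = 0.5.** The limits are c/√t and c, with c solving P(|Z₁| < c/√t, |Z₂| < c) = 0.95 and correlation √0.5 = 0.707.
- c = 1.977, so the final level is 0.0480, as in the SAP.
- 1.977/0.7071 gives an interim z of 2.797 (unrounded c), level 0.0052. The SAP has 0.002.
- Lan-DeMets spending at t = 0.5 gives about 0.0031/0.0490 (tails spent separately) or 0.0056/0.0478 (one two-sided function). Neither matches.
- Classical O'Brien-Fleming gives 0.002 only at t of about 0.41.
- 0.05 − 0.048 = 0.002. The overall level of the pair 0.002/0.048 at correlation 0.707 is 0.0486.

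**4. What each rule means as an observed HR.** With d events, SE(ln HR) ≈ 2/√d, so the limit is exp(−2z/√d). Under the design effect, 373 × (0.15 + 0.0945) = 91 events are expected; under the null, 112.

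| Rule | d = 91 | d = 112 |
|---|---|---|
| p = 0.0052 (z = 2.797) | HR 0.56 | HR 0.59 |
| p = 0.002 (z = 3.090) | HR 0.52 | HR 0.56 |
| observed HR 0.34 | z = 5.15, p ≈ 3 × 10⁻⁷ | z = 5.71, p ≈ 1 × 10⁻⁸ |

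Under the interim alternative itself, d = 373 × (0.15 + 0.053) = 76 and an observed HR of 0.34 has p ≈ 3 × 10⁻⁶. A plain comparison of the two proportions gives z = 0.097/√(2 × 0.1015 × 0.8985/373) = 4.39, p ≈ 1 × 10⁻⁵. On any of these counts it is far from 0.002.

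**5. Where 0.34 comes from.** ln(1 − 0.053)/ln(1 − 0.15) = 0.335. Power at 0.002 with 373 per arm is Φ[(0.097 − 3.090 × 0.0221)/0.0218] ≈ 90.5%, where 0.0221 and 0.0218 are the standard errors under null and alternative. So 0.34 is the effect detectable with about 90% power.

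**6. Chance of crossing for benefit if the true HR is 0.61, d = 91.** The drift is 0.494 × √91/2 = 2.358.
- At 0.0052: Φ(2.358 − 2.797) = 33%.
- At 0.002: Φ(2.358 − 3.090) = 23%.
- Under HR < 0.34: Φ[(ln 0.34 − ln 0.61) × √91/2] = Φ(−2.79) = 0.3%.

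**7. Final look.** exp(−2 × 1.977/√182) = 0.75 is the HR at which p = 0.048. An observed HR of 0.61 would have z = 0.494 × √182/2 = 3.33. If the true HR is 0.61, the estimate falls below 0.61 only about half the time, so 0.61 cannot be the rejection limit of a test with 90% power.

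**8. Information at 2.5 years.** Take P(event by u) = ∫₀ᵘ λe^(−λs)(1 − gs) ds, with λ = −ln(1 − rate) and g = 0 or 0.4. The constant hazard is an assumption. About 1862/3 = 621 people enrol between 1.5 and 2.5 years.
- No dropout, null: (139.7 + 47.8)/279.3 = 67% of events.
- 40% dropout, alternative: (91.6 + 33.8)/183.2 = 68%.

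At t = 0.68, Lan-DeMets spending (tails separate) gives about 0.013 and 0.046. The cost at the final look, by Schoenfeld with 182 events, is Φ(3.334 − 1.977) = 91.3% falling to Φ(3.334 − 1.995) = 91.0%.

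**The case against.** The strongest reply is that a severe interim was intended. The protocol wants a look that leaves final power almost untouched, and it compares the 65% interim effect with the meta-analytic estimates. At 0.0052 with 112 events the limit is HR 0.59, about the design effect itself, and a sponsor may reasonably prefer not to stop there. Both documents also leave stopping guidelines to discussion with the DMC and program leadership, and the protocol's section on premature termination refers to an efficacy boundary that the DMC establishes. Harm has other routes: excess serious adverse events or mortality are separate grounds for termination.

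Much of this stands. Severity is a legitimate choice, and harm is not blocked by the 2.94 limit. But the discussion with the DMC does not reconcile two contradictory rejection rules that are already written down, and a stricter boundary should not carry the name of a procedure with a different level.

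A reader might infer three stronger points, which the documents do not support:
- **That type I error is inflated.** It is not: 0.002/0.048 spends 0.0486. That 0.002 was obtained by subtraction is an inference, though the wording of SAP section 4.3 makes it plausible.
- **That the interim discards about a quarter of the events, and that this makes the boundary wrong.** SAP section 10.1 projects 746 subjects and calls them a sub-sample, but gives no exclusion rule. Section 10.2 defines information by observed events, and section 8.1 puts nearly everyone randomised into DMC reports. Even if only the 746 are analysed, t is 0.5 and 0.0052/0.0480 is the right pair. What remains is an ambiguity, and a loss of information (25 to 27% of events to date) if the narrow reading is meant.
- **That correcting the level alone would bring a large gain in the chance of stopping.** It moves 23% to 33%. Larger gains come from changing the data set as well.

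**Conclusion.** The point holds as a contradiction within the interim rule. The stated level of 0.002 is not the O'Brien-Fleming level at half information (0.0052), and the 0.34/2.94 limits are detectable effects written as critical values. Depending on which statement is followed, the chance of crossing under the design effect is about 33%, 23% or 0.3%. The same slip in SAP section 4.3 puts the final rejection limit at HR 0.61, where p = 0.048 is reached at about 0.75.

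Overall error control is not at risk, and the loss from the low interim level alone is modest. The HR limits are the more serious part, because read literally they nearly disable the interim and contradict the final test.

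These figures rest on the log-rank normal approximation with equal allocation. The crossing probabilities also assume 91 interim events. The 67 to 68% information figure assumes a constant hazard. The 95% interval planned beside a test at 0.048 is a small mismatch (95.2% would correspond) and does not affect the conclusion.

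**What to change.** In SAP section 10.1 and the protocol's Interim Analysis subsection, and wherever SAP sections 4.3 and 10 repeat the levels:

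1. State one interim boundary as a z or p value. If the interim uses only the first half of participants (t = 0.5), use z = 2.797, p = 0.0052, with final level 0.048. If it uses all events to date, specify O'Brien-Fleming-type spending at the observed event fraction, naming the spending function and how the tails are treated. If a stricter interim is wanted, state it as such without calling it O'Brien-Fleming.
2. Say whose data enter the interim, including participants still in follow-up, and use the same information fraction for efficacy and futility.
3. Remove 0.34/2.94 as rejection limits in both documents, and 0.61/1.64 in SAP section 4.3. Keep them, if useful, as detectable effects.
4. Optionally, report the final interval at the level that matches the final test.

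The cost is wording in two documents. Under spending at about 68% of events the final level falls from 0.048 to about 0.046, which costs under one percentage point of power.
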